7.1.3. Study Duration

The study is event driven and total duration will be determined by the time required to accrue approximately 121 primary endpoint events, estimated to be approximately 8 years. Subjects are expected to have a minimum follow-up time of approximately 6 years.

7.2. Number of Subjects

It is expected that approximately 350 subjects will be randomized in the study to achieve 121 adjudicated primary endpoint events.

7.3. Treatment Assignment

Subjects will receive either placebo or 5 mg OCA and should titrate to 10 mg OCA (in a blinded manner) at the 3-month study visit or at any study visit thereafter depending on tolerability.

7.4. Dose Titration Criteria

After 3 months of treatment at the 5 mg dose, the dose of OCA will be increased to the maximum dose of 10 mg OCA or matched placebo (in a blinded manner) at the 3-month visit or any study visit following the 3-month visit based on tolerability of investigational product. For those subjects that increased their dose to 10 mg, they may decrease his or her dose to 5 mg at any time during the study as considered appropriate (eg, tolerability), but should be titrated back to 10 mg based on tolerability and clinical judgment by the Investigator as soon as possible with the goal that all subjects remain on the 10-mg dose if tolerated.

7.4.1. Safety Criteria for Adjustment or Stopping Doses

Investigational product may be temporarily decreased (ie, from 10 mg to 5 mg daily, or by alternate day dosing) or temporarily or permanently stopped based on tolerability concerns. The dose of investigational product should be resumed to the maintenance dose in a blinded manner (5 mg or 10 mg) once the issues relating to the lack of tolerability are resolved.

Subjects that discontinue investigational product are expected to continue in the study (and follow the regular visit schedule) until the end of the study, and the study will only terminate at the time when the needed number of adjudicated events has accrued. If a subject reaches an event, he or she should continue the regular visit schedule and continue taking investigational product as long as the Investigator assesses it as safe. In general, subjects should be strongly encouraged to both stay on investigational product and remain in the study until study termination.

7.5. Criteria for Study Termination

The Sponsor reserves the right to terminate the study at any time. It is normal procedure to review the emerging clinical and safety data. As a result of such a review or a recommendation by the DSMC, it may be necessary to stop the study before all events have been accrued, and when subjects are still active on the study. In addition, the Sponsor may terminate the study at an investigational site at any time (eg, poorly performing sites, as determined by the number of subjects enrolled or the quality of the study data).

The Investigator and/or Sponsor (or designee) must notify the Institutional Review Board/Independent Ethics Committee (IRB/IEC) of discontinuation of a site or the study and the reason for doing so.

Investigators will be informed by the Sponsor as to when the final study visit is to be completed, and should then schedule all subjects for the End of Study Visit. The window of time for scheduling the visit will be based on a final projection of when the requisite 121 adjudicated events will have been accrued.

8. SELECTION AND WITHDRAWAL OF SUBJECTS

8.1. Subject Population

This study will be conducted at approximately 170 international study sites with experience in treating patients with PBC. Prospective subjects will be identified primarily from the hospital and/or physician's database of patients with PBC, or may be referred from other physicians. Patients may self-refer to an Investigator if they become aware of the study through local, national, or international PBC patient societies, forums, or networks.

8.2. Subject Inclusion Criteria

1. Definite or probable PBC diagnosis (consistent with AASLD and EASL practice guidelines; [Lindor 2009](#); [EASL 2009](#)), as demonstrated by the presence of ≥ 2 of the following 3 diagnostic factors:
 - History of elevated ALP levels for at least 6 months.
 - Positive antimitochondrial antibody (AMA) titer or if AMA negative or in low titer ($<1:80$) PBC-specific antibodies (anti-GP210 and/or anti-SP100 and/or antibodies against the major M2 components [PDC-E2, 2-oxo-glutaric acid dehydrogenase complex]).
 - Liver biopsy consistent with PBC.
2. A mean total bilirubin $>ULN$ and $\leq 3x ULN$ and/or a mean ALP $>5x ULN$
3. Age ≥ 18 years
4. Either is not taking UDCA (no UDCA dose in the past 3 months) or has been taking UDCA for at least 12 months with a stable dose for ≥ 3 months prior to Day 0.
5. Contraception: Female subjects must be postmenopausal, surgically sterile, or if premenopausal (and not surgically sterile), be prepared to use ≥ 1 effective method of contraception during the study and for 30 days after the end of treatment visit. Effective methods of contraception are considered to be those listed below:
 - Double barrier method, ie, (a) condom (male or female) or (b) diaphragm, with spermicide; or
 - Intrauterine device (IUD); or
 - Vasectomy (partner), or

- Hormonal (eg, contraceptive pill, patch, intramuscular implant or injection, or
 - Abstinence, if in line with the preferred and usual lifestyle of the subject)
6. Must provide written informed consent and agree to comply with the study protocol

8.3. Subject Exclusion Criteria

1. History or presence of other concomitant liver diseases including:
 - Hepatitis C virus infection
 - Active hepatitis B infection; however, subjects who have seroconverted (hepatitis B surface antigen and hepatitis B e antigen negative) may be included in this study after consultation with the medical monitor.
 - Primary sclerosing cholangitis
 - Alcoholic liver disease
 - Definite autoimmune liver disease or overlap hepatitis
 - Nonalcoholic steatohepatitis
 - Gilbert's Syndrome
2. Presence of clinical complications of PBC or clinically significant hepatic decompensation, including:
 - History of liver transplant, current placement on a liver transplant list, or current MELD score >12. Subjects who are placed on a transplant list despite a relatively early disease stage (for example per regional guidelines) may be eligible as long as they do not meet any of the other exclusion criteria.
 - Cirrhosis with complications, including history (within the past 12 months) or presence of:
 - Variceal bleed
 - Uncontrolled ascites
 - Encephalopathy
 - Spontaneous bacterial peritonitis
 - Known or suspected hepatocellular carcinoma
 - Prior transjugular intrahepatic portosystemic shunt procedure
 - Hepatorenal syndrome (type I or II) or Screening (visit 1 or 2) serum creatinine >2 mg/dL (178 µmol/L)
3. Mean total bilirubin >3x ULN
4. Subjects who have undergone gastric bypass procedures (gastric lap band is acceptable) or ileal resection or plan to undergo either of these procedures.

5. Other medical conditions that may diminish life expectancy, including known cancers (except carcinomas *in situ* or other stable, relatively benign conditions such as chronic lymphatic leukemia).
6. If female: plans to become pregnant, known pregnancy or a positive urine pregnancy test (confirmed by a positive serum pregnancy test by the central laboratory), or lactating.
7. Known history of human immunodeficiency virus infection.
8. Medical conditions that may cause non-hepatic increases in ALP (eg, Paget's disease or fractures within 3 months).
9. Other clinically significant medical conditions that are not well controlled or for which medication needs are anticipated to change during the study.
10. History of alcohol abuse or other substance abuse within 1 year prior to Day 0.
11. Participation in another investigational product, biologic, or medical device study within 30 days prior to Screening. Participation in a previous study of OCA is allowed with 3 months washout prior to enrollment in this study.
12. Mental instability or incompetence, such that the validity of informed consent or ability to be compliant with the study is uncertain.
13. History of known or suspected clinically significant hypersensitivity to OCA or any of its components.
14. UDCA naïve (unless contraindicated)

8.4. Subject Withdrawal from Investigational Product or Study Criteria

8.4.1. Reasons for Mandatory Discontinuation of Investigational Product

If a female subject becomes pregnant, she must discontinue taking investigational product, but should continue with the study visit schedule. The subject must be followed as considered appropriate by the Investigator and the medical monitor through pregnancy outcome. For reporting purposes pregnancy is not considered an AE. The subject may reinstate investigational product after delivery and cessation of breastfeeding (if applicable) at the discretion of the Investigator. Subjects whose pregnancy is terminated early (planned or unplanned) may be permitted to resume participation in the study if termination of the pregnancy is confirmed by a serum beta human chorionic gonadotropin (β -hCG) test performed at the central laboratory.

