7.1.2. Schedule of Study Procedures

Table 1: Schedule of Study Procedures

	Year 1								Years 2 through End of Study				
	Screening Visit 1 ^a	Screening Visit 2 ^a	Day 0	Safety Contact ^b	M 3	M 6	M 9	M 12	M 3 continued follow-up	M 6 continued follow-up	M 9 continued follow-up	M 12 continued follow-up	EOT/ EOS ^c
Visit Windows (+/-) ^d	3 to 8 wks prior to Day 0	1 to 6 wks prior to Day 0		±1 wk	±2 wks	±2 wks	±2 wks	±2 wks	±2 wks	±2 wks	±2 wks	±2 wks	±2 wks
STUDY PROCEDURES													
Informed Consent	X												
Medical/PBC History ^e	X												
Inclusion/Exclusion Criteria	X	X	X										
Physical Exam	X						X ^e					X ^e	X
Vital Signs (including weight)	X ^f		X		X	X	X	X ^f		X		X ^f	X ^f
12-Lead Electrocardiogram	X												X
Subject Questionnaires (5-D Pruritus Scale and Pruritus VAS)			X			X		X		X		X	X
Quality of Life Questionnaires (PBC-40, EQ-5D-5L, and FIS) ^g			X					X				X	X
TE Fibroscan [®] /DEXA ^h			X					X				X	X
Endoscopy ⁱ			X					X				X	
Hepatic Ultrasound ^j			X					X				X	X
Physical Exam and Assessments for Mayo Risk and Child-Pugh Scores ^k			X			X		X		X		X	X
Adverse Events	X	X	X	X	X	X	X	X	X	X	X	X	X
Prior and Concomitant Medications	X	X	X	X	X	X	X	X	X	X	X	X	X
Health Outcome Assessments ^l			X		X	X	X	X	X	X	X	X	X
Randomization/Treatment Assigned			X										

Table 1: Schedule of Study Procedures (Continued)

	Year 1								Years 2 through End of Study				
	Screening Visit 1 ^a	Screening Visit 2 ^a	Day 0	Safety Contact ^b	M 3	M 6	M 9	M 12	M 3 continued follow-up	M 6 continued follow-up	M 9 continued follow-up	M 12 continued follow-up	EOT/EOS ^c
Visit Windows (+/-) ^d	3 to 8 wks prior to Day 0	1 to 6 wks prior to Day 0		±1 wk	±2 wks	±2 wks	±2 wks	±2 wks	±2 wks	±2 wks	±2 wks	±2 wks	±2 wks
Dose Titration (if applicable) ^m					X								
Dispense Investigational Product ⁿ			X		X	X	X	X	X	X	X	X	
IP Accountability/Compliance				X	X	X	X	X	X	X	X	X	X
LABORATORY EVALUATIONS^o													
Urinalysis	X		X					X				X	X
Urine-based β-hCG Pregnancy Test ^p	X		X										
Chemistry/Hematology/Coagulation	X	X ^a	X		X	X	X	X	X	X	X	X	X
OCA, C4, and FGF-19 (plasma)			X		X	X	X ^q	X				X	X
Markers of Hepatic Fibrosis and/or Inflammation ^f			X			X		X		X		X	X
Genetics ^s			X					X				X	
Blood Sample for Future Analysis ^t			X			X		X		X		X	X

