β-hCG = beta human chorionic gonadotropin; DEXA = dual-emission X-ray absorptiometry; EOS= End of Study; EOT = End of Treatment; FGF = fibroblast growth factor-19; FIS= Fatigue Impact Score; IP = Investigational Product; M = month, wk = week

^a All subjects will have the chemistry panel retested to ensure subjects have 2 ALP and bilirubin assessments at least 2 weeks apart to calculate the mean result for both analytes.

The mean of all screening ALP and bilirubin assessments will be used to determine eligibility. Samples for hematology and coagulation will not be collected at Screening Visit 2.

^b The subject should be contacted by telephone on a monthly basis in between at-clinic study visits at Month 1 and Month 2 (±1 week), and also 2 weeks post dose titration (up or down), to assess for AEs and concomitant medications and to verify that s/he is dosing as directed.

^c As soon as possible upon study discontinuation and as near as possible to last dose taken.

^d Visits should be based on Day 0 (not on the prior visit).

^e Medical history at Screening and the yearly physical exam will include an assessment of smoking and alcohol consumption history and current habits for both.

^f Height will be collected at this visit.

^g The EQ-5D-5L and FIS Quality of Life questionnaires are validated for use in multiple languages. If a validated translation is not available in the local language required for a specific study subject, the data from that questionnaire will not be collected (See Section 11.1.2.2 and Section 12.2.6).

^h Transient elastography (TE) will be conducted at selected study sites where the Fibroscan® TE device is available. Similarly, DEXA will be conducted at selected study sites where the DEXA device is available. Please refer to Section 9.7.4 for additional information related to the allowed windows at Day 0 for these specific procedures.

-
- ⁱ Endoscopy will be conducted at selected study sites where the device is available to assess for the presence of oesophageal varix/varices. Please refer to [Section 9.7.4](#) for additional information related to the allowed window at Day 0 for this specific procedure.
 - ^j Ultrasound will be conducted to enhance HCC surveillance. If a lesion is found, a second confirmatory image (eg, MRI) should be obtained. Please refer to [Section 9.7.4](#) for additional information related to the allowed windows at Day 0 for this specific procedure

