 - ^k Child-Pugh Score will be calculated based on ascites assessment, hepatic encephalopathy grade, and central laboratory evaluations per the Child-Pugh scoring system noted in the case report form. Mayo Risk Score will be calculated based on central laboratory evaluations, diuretic use data, and peripheral edema assessment data captured in the CRF.
 - ^l Health Outcome Assessments: Data related to non-study related medical or surgical treatment procedures that the subject underwent and any medically relevant health care provider (HCP) or non-HCP related office visits that the subject attended should be collected throughout the study.
 - ^m After 3 months of treatment with investigational product, the dose should be increased (in a blinded manner) based on tolerability; this may occur at the Month 3 visit, or at any study visit thereafter. Titration above 10 mg OCA is not allowed.
 - ⁿ Subject to begin dosing on Day 1
 - ^o The subject should be instructed to fast overnight (at least 8 hours) prior to each visit (except Screening Visit 1). Fasting is required prior to all study visits, but water is permitted.
 - ^p Urine β -hCG pregnancy tests must be performed in females of childbearing potential prior to entry. If positive, a confirmatory blood test must be performed at the central laboratory. If the blood test is also positive, the subject may not be enrolled in the study. (Additional testing may be conducted where required, regionally).
 - ^q Only OCA PK samples will be collected at Month 9 at select study sites in a subset of subjects. Please refer to [Section 9.7.9](#) for the PK sampling schedule.
 - ^r Markers of hepatic fibrosis and/or inflammation are defined in [Section 11.1.2](#).
 - ^s A genetics study will be conducted in a subset of subjects who provide consent for analyses of these samples. Genetics samples will be collected at Day 0 and every other year beginning at Month 12
 - ^t Please refer to [Section 11.1.2.3](#) for description of the blood sample to be collected for future analysis.

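### Pregnancy is the one mandatory reason to stop study drug, but the protocol schedules no pregnancy test after Day 0 (minor subject-safety improvement)

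*Protocol*

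**What the plan says.** Section 8.4.1 (Amendment 1.1) contains one mandatory stopping rule for study drug: "If a female subject becomes pregnant, she must discontinue taking investigational product". The subject stays on the visit schedule, and follow-up of the pregnancy is left to the investigator and medical monitor.

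In Table 1 (Section 7.1.2, Amendment 1.1), the row "Urine-based β-hCG Pregnancy Test" is marked at Screening Visit 1 and Day 0 and is blank at every later visit, EOT/EOS included. The row "Dispense Investigational Product" is marked at Day 0 and at every quarterly visit after it. Footnote p says that "pregnancy tests must be performed in females of childbearing potential prior to entry" and adds "If positive, a confirmatory blood test must be performed at the central laboratory". On anything further it says only that "Additional testing may be conducted where required, regionally".

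The Month 3, 6 and 9 lists in Amendment 1.1 (Sections 9.7.6 to 9.7.8) contain no pregnancy test. The Amendment 1.1 text at hand stops at Section 9.7.9. For Month 12 and later the lists can be read only in Amendment 1 (Sections 9.7.10 to 9.7.14), and they contain none either. Table 1 of Amendment 1.1 is complete and settles the schedule.

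Section 8.2 admits premenopausal women who use contraception, with abstinence accepted. Section 8.3 excludes planned or known pregnancy.

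**The concern.** The protocol sets out what happens once a pregnancy is known: drug stops (8.4.1), the sponsor is notified (12.1.8, Amendment 1), and the EOT/EOS sequence is specified (Table 2 in 9.7.14, Amendment 1). All of this begins when someone learns of the pregnancy, and after Day 0 no scheduled test would reveal one.

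The stopping rule, the contraception requirement and the entry exclusion show that the protocol wants to avoid exposure in pregnancy. Yet a compliant site can raise the dose at Month 3 and resupply drug each quarter for years without testing. What is at stake is the safety of a small subset of subjects, not the efficacy inference.

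**Working it through.** The plan gives no figure to reproduce on this point, so the check is a count of scheduled visits plus simple interval arithmetic.

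**Inputs from the protocol**
- Minimum follow-up about 6 years and total duration about 8 years (Section 7.1.3).
- Quarterly visits, each ±2 weeks, anchored to Day 0 and not to the previous visit (Table 1 with footnote d; Section 9.7.1).
- Pregnancy test at Screening Visit 1 and Day 0 only; dispensing at each quarterly visit (Table 1).
- Urinalysis after Day 0 only at Month 12, the annual visits and EOT/EOS (Table 1).

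**Inputs assumed (not in the documents)**
- A full-length pregnancy of 40 weeks, with a range of 38 to 42.
- Start of pregnancy spread evenly over the year.
- The first days, when a urine test is still negative, are ignored.

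**Step 1. Visits and tests after Day 0.**
- 6 years × 4 = 24 quarterly visits and 0 scheduled tests.
- 8 years × 4 = 32 quarterly visits and 0 scheduled tests.

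**Step 2. Longest gap between tests if testing were added.** Because visits are anchored to Day 0, the windows do not accumulate.
- Quarterly: 13 weeks, or 13 + 2 + 2 = 17 at the window limits.
- Annual: 52 weeks, or 52 + 2 + 2 = 56 at the window limits.

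**Step 3. Average wait from the start of a pregnancy to the next test.**
- Quarterly: 13/2 = 6.5 weeks.
- Annual: 52/2 = 26 weeks.

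**Step 4. Share of pregnancies lying wholly between two annual tests.** For length L weeks at nominal spacing the share is (52 − L)/52.
- L = 40: 12/52 = 23%.
- L = 42: 10/52 = 19%.
- L = 38: 14/52 = 27%.

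**Step 5. The same question for quarterly tests.** A pregnancy of 38 to 42 weeks exceeds the 17-week maximum gap, so at least one scheduled test falls within it. One that ends before 13 weeks (before 17 at the window limits) can lie wholly between two tests. Section 8.4.1 itself foresees pregnancies that end early.

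Steps 2 to 5 compare possible remedies. They do not measure how many pregnancies go undetected under the present schedule, because the documents give no number of subjects who could become pregnant.

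**The case against.** Several objections have force.

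**No contradiction.** Section 8.4.1 says what to do when a pregnancy occurs; it does not promise surveillance. Footnote p makes pre-entry testing universal and leaves the rest to regional rules, an understandable division in a trial of about 170 international sites. This stands. A reader might infer that 8.4.1 and Table 1 conflict, but the text does not support that. The point is a weakness in the schedule.

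**Other scheduled contacts exist.** Adverse events and medications are reviewed at every visit, weight is taken regularly, a physical examination with oedema and ascites assessment takes place every six months, telephone contacts are planned, and medically relevant office visits are logged. A pregnancy or antenatal care could come to light at any of these. That lowers the risk and belongs in any fair account. But none is a pregnancy test, pregnancy is not treated as an adverse event (8.4.1), and adverse-event questioning is deliberately general (12.1.1.1, Amendment 1).

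**Exposure is not open-ended.** The absence of tests over 6 to 8 years might be read as unlimited fetal exposure. It is not. Exposure ends with the pregnancy at the latest, and many pregnancies would be recognised sooner.

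**Harm is not quantified.** The documents at hand report no reproductive toxicity, the Investigator's Brochure is not available, and the consent pages were removed. The mandatory stop justifies caution, but no size of harm can be claimed.

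**DEXA.** Footnote h limits the scan: "DEXA will be conducted at selected study sites where the DEXA device is available". The annual scan has no scheduled pregnancy test before it, but the documents give neither a count of DEXA sites nor a radiation risk. It is a secondary matter.

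**Conclusion.** The point holds as a minor subject-safety improvement. Outside regions that require further testing, the schedule lets a compliant site dispense drug quarterly during an unrecognised pregnancy with no scheduled pregnancy test, although pregnancy is the one mandatory reason to stop.

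Few subjects are likely to be affected: PBC is typically diagnosed between 40 and 60 years of age (Section 5.1), planned pregnancy is excluded and contraception is required. No number of pregnancies or scans is claimed. The primary analysis, power and type I error are untouched.

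The conclusion rests on Table 1 and footnote p of Amendment 1.1, and needs none of the assumptions about length of pregnancy; those bear only on the choice between quarterly and annual testing. A reader might also infer that quarterly testing would detect every pregnancy. It would not, because some that end early could still be missed.

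**What to change.** In the pregnancy-test row of Table 1, add a urine β-hCG test for women who could become pregnant at each quarterly dispensing visit, read before drug is handed out, and at EOT/EOS. Confirm a positive with the central-laboratory blood test already in footnote p, and hold drug until the result. Amend footnote p and the visit lists to match.

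At minimum, test at Month 12, each annual visit and EOT/EOS on the urine already collected there, and read the result before any DEXA. State that annual testing leaves the gap in Step 4 and so gives limited protection against exposure to study drug. A line in footnote h that DEXA is not done in a known pregnancy would be a small optional clarification.

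Cost of the full version: four dipsticks a year in a small subset, up to three of them needing a urine sample that Table 1 does not otherwise collect, and short drug holds on false positives. The minimum version costs one dipstick a year and one at EOT/EOS, with the same short hold on a false positive. No endpoint or analysis changes.
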